12.5.2 Storage of Study Devices

The study device must be stored in a secure area accessible to delegated study personnel only and administered only to subjects entered into the clinical study, at no cost to the subject, in accordance with the conditions specified in this protocol.

VOLUMA with Lidocaine must be stored at [REDACTED] with a continuous temperature monitoring device (provided by Allergan, if necessary). Use of the temperature monitoring device is required to ensure that the study product is being maintained within the acceptable storage-range conditions. If the storage temperature varies from the programmed limits, the monitoring device alarm will trigger indicating an excursion that may impact the stability of the study product. Sites must report any alarmed temperature excursion to Allergan, and avoid administering the impacted study product, by isolating the product, until receiving further instructions from Allergan. Do not freeze or expose to extreme heat. Do not use if the package is open or damaged or if the product is not clear.

12.5.3 Study Device Accountability

The TI (or designee) must keep an accurate accounting of the number of study devices received from Allergan, dispensed to subjects, and returned to Allergan (or designee) during and at the completion of the study. A detailed inventory must be completed for the study devices including subject initials, device serial/lot number, date of implantation, and date of explantation if applicable. The study product must be administered to study subjects by a TI only.

12.5.4 Return of Study Devices

Upon completion of the treatment period, the quantities of all used and unused study devices will be reconciled. The blister/outer packaging of used syringes will be retained for verification against the eCRF by Allergan's study monitor. The used syringes will be destroyed appropriately at the site by following the site's routine internal practices and China local regulations. Unused syringes of VOLUMA with Lidocaine will be returned to an Allergan-contracted local depot in China for destruction according to Allergan instructions.

Devices that are damaged during shipment or at the site or that malfunction during use (eg, faulty syringe or plunger) must be accounted for, and the nature of the malfunction will be recorded on the appropriate form. The TI (or designee) will promptly notify Allergan's Medical Safety Physician or Clinical Research Department of any device malfunction. Any faulty syringe will be sent to an Allergan-contracted local depot in China for destruction.

12.6 Monitoring by Allergan

Appropriately trained representatives of Allergan will monitor the conduct of the trial at each investigational site, including visits to the site to review, verify, and retrieve copies of study-related documents. It is the responsibility of the Principal Investigator (or designee) to be present or available for consultation and to assure that Allergan has access to all study-related records during scheduled monitoring visits.

Allergan will review device accountability records and completed eCRFs to ensure completeness and consistency with the source records and compliance with the protocol requirements.

12.7 Testing of Biological Specimens

At screening and at month 6 posttreatment, blood samples will be collected and prepared for routine hematology and chemistry testing by a central laboratory located in China.

Routine hematology tests including:

- levels of hemoglobin and hematocrit, concentration of red blood cells, mean cell volume, mean cell hemoglobin, mean cell hemoglobin concentration, red blood cell morphology, and the concentration of white blood cells, neutrophils (% absolute), lymphocytes (% absolute), monocytes (% absolute), eosinophils (% absolute), basophils (% absolute), and platelets

Chemistry tests including:

- hepatic function tests: total bilirubin, direct bilirubin, alkaline phosphatase, alanine aminotransferase, aspartate aminotransferase, gamma-glutamyl transpeptidase, total protein, and albumin
- renal function tests: urea nitrogen, creatinine, uric acid, calcium, and phosphorous
- others: lactate dehydrogenase, glucose, triglycerides, cholesterol, and creatinine kinase

At screening and at month 6 posttreatment, urine samples will be collected for routine macro and micro panel of tests conducted by the central laboratory in China to assess color and clarity, specific gravity, pH, and concentration of protein, glucose, ketones, bilirubin, urobilinogen, blood, nitrite, and leukocyte esterase, and for microscopic analysis.

At screening, on treatment days prior to injection, and at study exit, a trained research staff member at each investigational site will perform pregnancy testing on urine samples from women of childbearing potential. The urine pregnancy test employed will test for the presence of human chorionic gonadotropin and should have a sensitivity of at least 50 mIU/mL.

All blood and urine samples (ie, not including samples for urine pregnancy testing) will be stored at the central laboratory for the duration of the study. The central laboratory will be responsible for sample destruction when the study sites have been closed. Allergan shall have full ownership rights to any biological specimens/samples derived from the study.

12.8 Publications

This study will be registered and results posted on www.clinicaltrials.gov. Allergan, as the sponsor, has proprietary interest in this study. Authorship and manuscript composition will reflect joint cooperation between study Investigators and Allergan personnel. Authorship will be established prior to the writing of the manuscript. As this study involves multiple centers, no individual publications will be allowed prior to completion of the final report of the multicenter study except as agreed with Allergan.

Version Date/ Amend. No.	Changes to Protocol
	
 • [REDACTED] • Section 6.2.2.1 - clarified anatomical characteristics measurements; added “nasal root height, nasal length, and ala depth”, and deleted “nasofacial angle” • Section 6.2.2.2 - 28-day post-treatment subject diary updated to 56-day post-treatment subject diary, routine follow-up visits for safety and effectiveness updated from Weeks 4 and 12 to Weeks 8 and 16 • Section 6.2.2.3 – timing of control group assessments updated from Weeks 4 and 12 to Weeks 8 and 16 • Section 6.2.3.2 – timing of touch-up treatment updated from 4 to 8 weeks • Section 6.3 - 28-day post-treatment subject diary updated to 56-day post-treatment subject diary • [REDACTED] • Section 7.2 - 28-day post-treatment subject diary updated to 56-day post-treatment subject diary throughout • Section 7.5 - 28-day post-treatment subject diary updated to 56-day post-treatment subject diary • Section 8.5 - added “In order to have over 100 treatment group subjects complete 1 year follow-up”, clarified subject attrition of 15% “during the whole study duration” • Section 9.1.3 –timing of treatment sessions updated from 4 to 8 weeks apart • Section 14 – 28-day post-treatment subject diary updated to 56-day post-treatment subject diary • Section 15 – added protocol amendment summary

Approval Date: 22-Sep-2017

| JUVI | DEKIM | VOLC | IVIA WIL | II LIUOCAIIIC | |
|------|--------|--------|------------|----------------------------------|----|
| | | 6.3.3. | Protocol | Deviations | 25 |
| | | 6.3.4. | Medical | History | 26 |
| | | 6.3.5. | Prior/Co | ncomitant Medications | 26 |
| | | | | | |
| | | | | | |
| | | | | | |
| | | | | | |
| | | | | | |
| | | | | | |
| | 6.4. | Data H | Iandling C | Convention | 28 |
| | | | _ | Window | |
| | | | | Effectiveness | |
| | | | 6.4.1.2. | Safety | 29 |
| | | 6.4.2. | | Date Imputation | |
| | | | | Missing/Incomplete AE Start Date | |
| | | | | Missing/Incomplete AE End Date | |
| 7. | Refere | nces | | | 31 |
| | | | | | |

List of Tables

| Table 4–1 | Analysis Populations | 12 |
|-----------|--|----|
| Table 5-1 | CP and TP definition | 13 |
| Table 5–2 | Sensitivity Analyses of Primary endpoint. | 16 |
| Table 5–3 | Secondary Effectiveness Analyses | 17 |
| | | |
| Table 5–5 | Exposure to Study Treatment. | 19 |
| Table 5–6 | Administration of Study Treatment | 19 |
| Table 5-7 | TEAE Summaries | 20 |
| Table 5-8 | ISR Analyses | 21 |
| Table 5-9 | Procedural Pain Analyses | 21 |
| Table 6-1 | Protocol Deviation Summary | 26 |
| Table 6-2 | Prior and Concomitant Medications | 26 |
| Table 6-3 | Effectiveness Analysis Visit Definitions for Treatment Group during Control Period and Treated Period. | 29 |
| Table 6-4 | Effectiveness Analysis Visit Definitions for Control Group during Control Per | |
| Table 6-5 | Effectiveness Analysis Visit Definitions for Control Group during Treated Per | |
| Table 6-6 | Imputation Scenarios | 30 |

SAP Version History

This SAP for study 1894-701-008 is based on the protocol Amendment 1 (dated 22-Sep-2017).

| | SAP Version History Summary | | | | | |
|----------------|-----------------------------|---|---|--|--|--|
| SAP Version | Approval Date | Change | Rationale | | | |
| 1 | August 13, 2019 | Not Applicable | Original version | | | |
| 2 | | Baseline definition for efficacy analysis in control group | Including participants with baseline 3D photos taken after randomization due to Canfield setting-up error | | | |
| | | Add a rule of analysis for participants who have two measurements at one visit in Section 6.4.1 | Dealing with data issues: some participants have more than one photo taken at one visit | | | |
| | | Add explanation of analysis population definition change | Providing justification of the changes | | | |
| | | Wording change: "subject" to "participant" | Following internal new guidance | | | |
| | | Change VITP to VOLUMA; VOTP to VOLUMA Post- Control in Table 5.1 | Being consistent with wording in shell | | | |

1. Introduction

This SAP provides a more technical and detailed elaboration of the statistical analyses of the effectiveness and safety data as outlined and specified in study 1894-701-008 protocol Amendment 1 (approved version dated 22-Sep-2017). Specifications of tables, figures, and data listings are contained in a separate document.

1.1. Objectives and Endpoints

| Objective | | | | | |
|---|---|---|--|--|--|
| Clinical | Statistical | | | | |
| Category | Category | Estimand/Variable | | | |
| Primary Objecti | ve: to evaluate th | ne safety and effectiveness of VOLUMA with Lidocaine injectable gel for the | | | |
| improvement of v | olume and aesthe | etic appearance of the nose in a Chinese population. | | | |
| Effectiveness ¹ | Variable: change from baseline in the nose volume calculated by | | | | |
| | | digital analysis of each participant's 3D images at Week 24 | | | |
| | | Population: mITT | | | |
| | | • IES: | | | |
| | | Missing at random will be assumed in an MMRM model, | | | |
| | | therefore no imputation will be conducted | | | |
| PLS: change from baseline between treatment and MMRM | | • PLS: change from baseline between treatment and control groups | | | |
| | | o MMRM | | | |
| | Secondary | Variable: GAIS responder by EI and participant, NSS responder by | | | |
| | | participant at Week 24 | | | |
| | | Population: mITT | | | |
| | | • IES: | | | |
| | | Participants with missing data at Week 24 will not be imputed | | | |
| | | PLS: responder rates between treatment and control groups | | | |
| | | o Fisher's exact test | | | |
| Safety | Primary | Variable: | | | |
| | | o TEAEs | | | |
| | | o ISRs | | | |
| | | Population: Safety Population | | | |
| | | Analysis: Categorical descriptive | | | |

IES = Intercurrent event(s) strategy; PLS = Population-level summary.

¹ All estimand attributes explicitly identified for primary/secondary and select key estimands only.

1.2. Study Design

Study 1894-701-008 is a prospective, multicenter, randomized, "no treatment" control design study to evaluate the safety and effectiveness of JUVÉDERM® VOLUMA® with Lidocaine injectable gel (hereafter, VOLUMA with Lidocaine) to improve the volume and aesthetic appearance of the nose in Chinese adults.

The following treatment groups are defined for this study:

- Study Treatment: JUVÉDERM® VOLUMA® with Lidocaine Injectable Gel
- Control Treatment: No-treatment

[figure not shown]
This trial consists of 2 periods: Control Period and Post-Control Period.

Participants will be randomized in a 3:1 ratio either to have treatment with VOLUMA with Lidocaine at the outset of the study (treatment group) or a 24-week control period followed by optional delayed treatment (control group).

At least 160 participants will be randomized at up to 9 investigational sites.

No interim analyses are planned for this study.

The Schedule of Visits and Procedures during the study are presented in Table 1–1, Table 1–2, and Table 1–3.

JUVÉDERM® VOLUMA® with Lidocaine

2. Statistical Hypotheses

The null hypothesis is that there is no difference between the treatment group and the control group in mean change from baseline in volume in nose area based on 3D imaging. The alternative hypothesis is that there is a difference in mean change from baseline in volume in nose area based on 3D imaging between that treatment group and control group.

Ho:
$$\mu T = \mu C$$
 versus Ha: $\mu T \neq \mu C$

where μ T and μ C denote the mean change in volume from baseline for the treatment group and control group, respectively, at Week 24.

The hypotheses will be tested using an MMRM model with change from baseline in nose volume as the response variable, with treatment, timepoint (visit of Weeks 8, 16, and 24), treatment-by-timepoint interaction as fixed effect. Participant will be included in the model as a random effect.

3. Sample Size Determination

A sample size of 90 treatment and 30 control participants will provide 99.6% power to detect a difference of 0.9 mL in the mean volume change from baseline between the treatment and control group, assuming a mean change from baseline of 1.1 mL with standard deviation of 0.9 mL, and mean change from baseline of 0.2 mL with standard deviation of 0.9 mL, for the treatment and control groups, respectively. This calculation is based on a 2-sample, 2-sided t-test at 5% significance level. The assumptions of means and standard deviations are estimated from Allergan studies VOLXC-AP-ND-001 and VOLUMA-004. In order to have over 100 treatment group participants complete 1-year follow-up, accounting for participant attrition of 15% during the whole study duration through Week 48, at least 120 participants in the treatment group and 40 participants in the control group will be randomized.

4. Populations for Analysis

The analysis populations will consist of participants as defined in Table 4–1:

Table 4–1 Analysis Populations

| Population | Definition | Study Treatment | |
|---|--|--------------------|--|
| mITT Population | mITT Population All participants who are randomized and have at least 1 assessment of change from baseline in nose volume | | |
| PP Population | All mITT participants who have baseline and Week 24 assessments of | | |
| Safety Population | All randomized participants who receive VOLUMA treatment in the Control Period or who do not receive VOLUMA treatment in the Control Period and with at least 1 follow-up assessment | As treated | |
| VOLUMA Initial Treated Population (VITP) | Participants randomized and received VOLUMA treatment in the Control Period with up to 48 weeks follow-up | As treated | |
| VOLUMA Optionally Treated Population (VOTP) | Participants randomized to control group and received optional VOLUMA treatment in Post-Control Period. These participants will have up to 24 weeks follow-up after optional VOLUMA treatment (or touch-up treatment). | As treated | |

JUVÉDERM® VOLUMA® with Lidocaine

5. Statistical Analyses

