8.1 Analysis Populations

The following analysis populations will be used in the analyses for this study:

- modified intent-to-treat (mITT) population: subjects who are randomized to study treatment, receive at least 1 study device treatment and complete at least 1 effectiveness assessment (Treatment Group); and subjects who are randomized to no treatment and complete at least 1 effectiveness assessment (Control Group)
- per-protocol (PP) population: all mITT subjects who do not have any significant protocol deviations affecting the primary effectiveness endpoint
- safety population: subjects who receive at least 1 study treatment

Unless specified otherwise, effectiveness analyses and baseline characteristics will be conducted using the mITT population. The PP population will be used to perform sensitivity analyses for the primary effectiveness variable. All safety analyses will be conducted using the safety population. Control subjects' data after treatment will also be summarized.

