5.1. General Considerations

- The primary analysis will be performed after the database is locked and randomization schedule is released.
- Participants will receive treatment at the outset of the study (treatment group) or have treatment delayed until Week 24 (control group). The delayed treatment for control group is optional and referred to as "Optional Treatment".
- Control Period (CP), Treated Period (TP) are defined in Table 5-1.

Table 5-1 **CP and TP definition**

| Randomization | Period | Treatment | Start Date | End Date |
|---------------|--------|------------------------|---------------------------------|---|
| Group | | Group Label | | |
| Treatment | СР | VOLUMA | Initial treatment date | The date of effective assessment for Week 24. If multiple assessments fall into Week 24 window, the date of the assessment included in the Week 24 analysis will be used as end date. For participants who exit before Week 24, the end date is study exit date. For participants with intermittent missing assessment at Week 24, the target day for Week 24 (Day 169) will be the end day. |
| | TP | VOLUMA | Initial treatment date | Study exit date |
| Control | СР | Control | Randomization date | For participants who do not receive optional treatment If multiple assessments fall into Week 24 window, the date of the assessment included in the Week 24 analysis will be used as end date. For participants who exit before Week 24, the end date is study exit date. For participants with intermittent missing assessment at Week 24, the target day for Week 24 (Day 169) will be the end day. For participants who receive optional treatment: The day before optional treatment |
| | ТР | VOLUMA Post-Control | Optional initial treatment date | Study exit date |

JUVÉDERM® VOLUMA® with Lidocaine

- For CP, effectiveness analyses and baseline characteristics will be performed on the mITT population using the "as-randomized" assignment. One of the sensitivity analyses for the primary endpoint will be based on PP population. Safety analyses for CP will be conducted using the Safety Population based on "as-treated" assignment.
- For TP, effectiveness and safety summaries will be performed on the VITP and VOTP using "as-treated" assignment.
- For applicable effectiveness endpoints, baseline is defined as the last non-missing value prior to the start of study treatment for treatment group or no later than randomization date for control group.

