5.4.2. Main Analytical Approach

[figure not shown]
The secondary effectiveness endpoints will be analyzed using Fisher's exact test based on mITT population as observed.

The exact binomial 95% CI will be provided for the proportion of responders within each treatment group. For comparison of treatment group versus control group at Week 24, the responder rate difference, 95% exact unconditional CI for risk difference, and p-value from 2-sided Fisher's exact test will be presented.

Secondary effectiveness analyses are summarized in Table 5–3.

Table 5–3 Secondary Effectiveness Analyses

| Endpoint | Description | Timing | Methodology | |
|---------------------------|--|---------|---------------------|--|
| Responder status based on | nder status based on Number (%) of responders by Week 24 | | Fisher's exact test | |
| GAIS by EI | treatment group | WCCK 24 | Fisher's exact test | |
| Responder status based on | Number (%) of responders for | Week 24 | Fisher's exact test | |
| GAIS by participant | treatment group | WEEK 24 | risher s exact test | |
| Responder status based on | Number (%) of responders for | Week 24 | Eigher's exect test | |
| NSS by participant | treatment group | week 24 | Fisher's exact test | |

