6.2. Appendix 2: Changes to Protocol-Planned Analyses

In this SAP, the primary analysis will be done by an MMRM. The original primary analysis in Protocol 1894-701-008 Amendment 1 was based on observed data. The original analysis based on observed data will be included as one of the sensitivity analyses.

The definition of mITT is changed from "Subjects who are randomized to study treatment, receive at least 1 study device treatment and complete at least 1 effectiveness assessment (Treatment Group); and subjects who are randomized to no treatment and complete at least 1 effectiveness assessment (Control Group)" in protocol to "All participants who are randomized and have at least 1 assessment of change from baseline in nose volume" in SAP. The changes make it clear that participants need to have at least one primary effectiveness variable (purpose of effectiveness assessment). Participant who are randomized to treatment but don't receive study device treatment will be withdrawn from the study and have no any follow-up visits. So device treatment requirement was not necessary and excluded from definition in SAP for simplicity.

The definition of PP is changed from "All mITT subjects who do not have any significant protocol deviations affecting the primary effectiveness endpoint" in protocol to "All mITT participants who have baseline and Week 24 assessments of change from baseline in nose volume and do not have any significant protocol deviations affecting the primary effectiveness endpoint" in SAP. This change adds one requirement for the availability of primary endpoint in line with key criteria of PP definition in ICH E9.

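### The SAP's volume-based mITT drops observed Week 24 GAIS and NSS ratings from the secondary analyses when a participant has no nose-volume change at any visit

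*SAP*

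**What the plan says.** **Protocol 8.1** admits a treated participant to mITT on these conditions: "receive at least 1 study device treatment and complete at least 1 effectiveness assessment (Treatment Group". For controls it takes "subjects who are randomized to no treatment and complete at least 1 effectiveness assessment (Control Group". Any effectiveness assessment qualifies, so a GAIS or NSS rating is enough.

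**SAP section 4, Table 4–1** replaces this with "All participants who are randomized and have at least 1 assessment of change from baseline in nose volume".

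**SAP 6.2 (Appendix 2)** discloses the change and gives its reason: "The changes make it clear that participants need to have at least one primary effectiveness variable". It does not mention the secondary endpoints.

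**SAP 5.1** sets the population for the Control Period: "For CP, effectiveness analyses and baseline characteristics will be performed on the mITT population using the 'as-randomized' assignment". **SAP 5.4.2** repeats it for the secondary endpoints: "The secondary effectiveness endpoints will be analyzed using Fisher's exact test based on mITT population as observed". The objectives table in SAP 1.1 also lists mITT for them.

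**SAP 5.4.1** defines responders for all three endpoints as a score of 1 or 2 on a 5-point rating at Week 24. Volume plays no part.

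**The concern.** The population filter is applied before the as-observed rule. A participant can have a valid Week 24 rating and still be left out, because of an imaging failure that belongs to a different endpoint. The only reason given for the filter concerns the primary variable. The visible SAP text offers no rating-based population and no sensitivity analysis for GAIS or NSS.

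The study objective covers both volume and aesthetic appearance, and the ratings carry the second part. At stake are the completeness of those analyses and their agreement with the population that the protocol specified. The primary result is not affected.

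**Working it through.** The point rests mainly on reading the definitions together. A short calculation then gives the scale.

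**Step 1. Who is removed.** A volume change needs a baseline image and at least one follow-up image, both usable. Table 4–1 asks for one such change at any visit. Protocol 6.2.2.2 and 6.2.2.3 schedule imaging at Weeks 8, 16 and 24 in both arms.

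| Imaging status of a Week 24 rater | In the SAP mITT? |
|---|---|
| Week 24 image missing, Week 8 or 16 usable | Yes |
| No usable follow-up image at any visit | No |
| No usable baseline image | No |

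**Step 2. Which endpoints are exposed.**
- *NSS.* Protocol 6.2.2.2 has the participant rate satisfaction using a mirror, with no photo comparison stated. The rating does not depend on imaging.
- *GAIS, both raters.* The same section has it rated live (EI) or in a mirror (participant), by comparison with baseline photos. With no baseline photo at all, the rating itself may be compromised. The problem remains where a photo supports the rating but not the volume analysis, or where only the follow-up images failed.
- *Control arm.* Protocol 6.2.2.3 schedules only EI GAIS for controls in the Control Period. (Protocol 8.3.2 says controls will have no GAIS data then. I follow the schedule.) Participant GAIS and NSS have no scheduled control ratings to lose.

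**Step 3. The plan's own figures.** The plan gives no number for this point. Its completer figures reproduce: 120 × 0.85 = 102 treated, 40 × 0.85 = 34 controls, 160 × 0.85 = 136 in total. The stated 99.6% power also reproduces closely (99.70% by the exact t calculation with 90 and 30 participants). Neither the concern nor the fix changes these.

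**Step 4. Scale.** Let N participants in an arm have a Week 24 rating and let k of them be excluded. Let p_r be the responder rate among those retained and p_e the rate among those excluded.

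Rate in all rated = [(N − k) × p_r + k × p_e] / N

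mITT rate minus rate in all rated = (k/N) × (p_r − p_e)

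The shift can never exceed k/N. The documents do not give N at Week 24. The figure of 102 comes from 15% attrition through Week 48, so I show 102 and the full 120. The values of k are assumptions. The last two columns also assume N = 102 and a retained rate of about 80% (81/101, 79/99, 78/97, 74/92), with p_e anywhere from 0 to 100%.

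| k | Bound k/102 (points) | Bound k/120 (points) | mITT too high by at most | mITT too low by at most |
|---|---|---|---|---|
| 1 | 1.0 | 0.8 | 0.8 | 0.2 |
| 3 | 2.9 | 2.5 | 2.3 | 0.6 |
| 5 | 4.9 | 4.2 | 3.9 | 1.0 |
| 10 | 9.8 | 8.3 | 7.9 | 1.9 |

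Example, k = 5: 5/102 × 78/97 = 3.9 points; 5/102 × 19/97 = 1.0 point.

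For EI GAIS in the control arm, one exclusion moves the rate by at most 1/34 = 2.9 points, or 1/40 = 2.5 points if all 40 are rated.

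**The case against.** The other side has a good deal to say.

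- *The route to exclusion is narrow.* Protocol 6.2.2.1 requires baseline imaging before randomization, 10.1.1 excludes people who decline photos, and 6.4 allows poor images to be repeated. One usable pair at any visit suffices. This stands, and it is why the number is probably small.
- *The version history records a repair.* A reader might take the camera set-up error as proof that participants were lost. The entry gives the reason for the version 2 change to the control baseline rule as "Including participants with baseline 3D photos taken after randomization due to Canfield setting-up error". SAP 5.1 now accepts a control baseline up to and including the randomization date, so a photo taken later that day counts. A photo from a later date would not, but the documents do not say that any exists.
- *Ratings are not lost from all reporting.* VITP requires treatment, not a volume value, and SAP 5.1 uses it for Treated Period effectiveness summaries. That period starts at initial treatment and so covers Week 24. Treated participants' ratings can still appear there. This stands; the loss is from the specified secondary analysis.
- *One common set for primary and secondary endpoints is defensible, and the change is disclosed.* The disclosure stands. The reason given covers only the primary variable, though, and the visible text does not argue for a common set.

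**Conclusion.** The point holds in a limited form. The SAP excludes from all three secondary analyses any participant who has an observed Week 24 rating but no nose-volume change at any visit. It gives no reason that applies to those endpoints. The case is clearest for NSS in the treatment group, partial for GAIS, and confined to EI GAIS among controls.

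The number affected is not in the documents and may be zero. The effect on a responder rate is at most k/N, about 1 point per treated participant excluded if 102 are rated. The tabulated shifts rest on assumed counts and an assumed responder rate, so they show scale and are not estimates.

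Two stronger readings should be set aside. A reader might infer that a missing Week 24 image is enough to exclude; Table 4–1 does not say so. A reader might also infer that the control arm suffers most. Each control does carry more weight, but two of the three endpoints have no scheduled control ratings in that period, and nothing in the documents points to losses that differ by arm.

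This is a minor point, worth acting on because the correction is cheap.

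**What to change.** Keep the volume-based mITT for the primary MMRM and for the baseline tables, so that those tables still describe the primary-analysis set.

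In SAP 1.1, 4 and 5.4.2, state that each secondary endpoint is analysed as randomized, in all randomized participants with an observed Week 24 rating for that endpoint, whether or not a volume change is available. Align the general statement in SAP 5.1. Report N per endpoint and arm.

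The protocol's treatment-received condition need not return: Appendix 2 explains that participants randomized to treatment but not treated are withdrawn and have no follow-up visits.

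The cost is one extra population flag, a few lines of SAP text, and denominators that may differ slightly between the primary and secondary tables. No sample size or power figure changes.
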